All participants who are approached for this study will already be participating in the prospective observational Cohort Study 212914, also running at the same trial sites. Participants will attend a study site visit at Screening and Day 1 (Baseline) before starting daprodustat (study intervention) at the end of Day 1 assessments. To allow flexibility, Screening and Day 1 Visits can be conducted up to 4 weeks apart but may also be performed on the same day. Blood tests for eligibility checked at Screening do not need to be repeated if the Day 1 Visit is performed within 7 days of the Screening Visit. After commencement of daprodustat, participants will be seen at Week 2 and Week 4 Visits to assess the initial safety and Hgb response to daprodustat. Further visits while participants remain on daprodustat are scheduled at 4-weekly intervals up to Week 28, then every 8 weeks up to Week 52. There is a Follow-up Visit at Week 56, 4 weeks after the last dose of daprodustat. Between Weeks 28 to 52, an extra Hgb check visit should be undertaken if a dose change has been made and the next scheduled visit is not within 4 weeks. An unscheduled (UNS) visit (at any time during the study) may be conducted if, in the opinion of the investigator, the participant would benefit from additional monitoring of Hgb sooner than the next scheduled visit (within 4 weeks) and/or for other parameters or if there is a safety concern.

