#### 1.3. Schedule of Activities

The Schedule of Activities (SoA) is presented in Table 1.

Table 1 Schedule of Activities

							Treatme	nt Period	I						gb Check lisit	Early Discontinuation	Follow -up
Procedure	Screening (-4 weeks to Day 1)	Day 1	Week 2 (± 3 days)	Week 4 (-7 to +2 days)	Week 8 (-7 to +2 days)	Week 12 (-7 to +2 days)	Week 16 (-7 to +2 days)	Week 20 (-7 to +2 days)	Week 24 (-7 to +2 days)	Week 28 (-7 to +2 days)	Week 36 (-7 to +2 days)	Week 44 (-7 to +2 days)	Week 52 (-7 to +2 days)	UNS at Any Time Day 1 to Week 56 a	4-weekly if needed (Weeks 32, 40 & 48) b	from Study Intervention / Withdrawal Visit	Week 56 (-7 to +2 days)
Informed consent	Х																
ELIGIBILITY ASS	SESSMENTS																
Inclusion and exclusion criteria	х	Х															
Demography	Х																
Medical and treatment history	Х																
12-lead ECG c	Х																
SAFETY ASSESS	SMENTS																
AE/SAE assessment	Х	Х	Х	Х	Х	Х	Х	Х	Х	Х	Х	Х	Х	Х	Х	Х	х
Vital signs (BP, HR) d	Х	Х	Х	Х	Х	Х	Х	Х	Х	Х	Х	Х	Х	Х	Х	Х	Х
Height, weight e	Х	Х	Х	Х	Х	Х	Χ	Х	Х	Χ	Х	Х	Х	Х	Х	Х	Х
Physical exam	Х	Х				Χ			Х		Х		Х	X a		Х	Х

214066 Protocol Amendment 02

							Treatme	nt Period	I					Extra Hgb Check Visit		Early Discontinuation	Follow -up
Procedure	Screening (-4 weeks to Day 1)	Day 1	Week 2 (± 3 days)	Week 4 (-7 to +2 days)	Week 8 (-7 to +2 days)	Week 12 (-7 to +2 days)	Week 16 (-7 to +2 days)	Week 20 (-7 to +2 days)	Week 24 (-7 to +2 days)	Week 28 (-7 to +2 days)	Week 36 (-7 to +2 days)	Week 44 (-7 to +2 days)	Week 52 (-7 to +2 days)	UNS at Any Time Day 1 to Week 56 a	4-weekly if needed (Weeks 32, 40 & 48) b	from Study Intervention / Withdrawal Visit	Week 56 (-7 to +2 days)
Tanner staging		Х											Х			Χf	
LABORATORY	ASSESSMEN	TS		•	•	•	•	•	•		•	•					
Hgb (full blood count)	Х	Х	Х	Х	Х	Х	Х	Х	Х	Х	Х	Х	Х	X g	Х	Х	Х
Iron parameters (TSAT, ferritin)	Х	Х		Х	Х	Х	Х	Х	Х	Х	Х	Х	Х	X g	X g	X	Х
Creatinine, urea/BUN, potassium, sodium, calcium	Х	Х		Х	Х	Х	Х	Х	Х	Х	Х	Х	Х	X a	X a	Х	Х
LFTs (+INR h)	Х	Х		Х	Х	Х			Х		Х		Χ	X g	X g	Х	Х
Pregnancy test (FOCBP only) i, l	Х	Х	Х	Х	Х	Х	Х	Х	Х	Х	Х	Х	Х	X g	X g	Х	Х
PK Sampling (Optional unless in the Integrated PK Phase)		Χj	X k	X k													

214066 Protocol Amendment 02

							Treatme	nt Period							gb Check isit	Early Discontinuation	Follow -up

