#### NOTE:

- All visit timings are relative to Day 1. Daprodustat will be dispensed to cover the visit period (plus permitted time window) at each dispensing visit. An IRT transaction will be
  required to dispense daprodustat. Additional IRT transactions may occur to dispense additional daprodustat in case replacement is needed.
- Blood tests for eligibility checked at Screening do not need to be repeated if the Day 1 Visit is performed within 7 days of the Screening Visit.
- All Day 1 procedures will be before the first of dose of daprodustat, except for post dose PK sampling on Day 1 (which occurs at the end of Day 1 once a participant is confirmed
  as eligible and is enrolled into the study). PK sampling is required for those participants in the Integrated PK Phase, otherwise PK sampling is optional.
- a. An unscheduled (UNS) /extra check Hgb Visit may be conducted at any time during the study if, in the opinion of the investigator, the participant would benefit from additional monitoring of Hgb and/or other parameters if clinically indicated.
- From Week 28, an extra Hgb check Visit should be arranged 4 weeks after the last dose visit if:
  - At the last study visit:
    - o there was a dose change
    - o if dosing was temporarily withheld as Hgb >12.5 g/dL
    - o a dose reduction was needed but the participant was on lowest dose already
  - Since the last study visit the following occurred:
    - o a moderate CYP2C8 was prescribed
    - o a rhEPO or analogue was given in error
    - o a Hgb check performed outside of the study indicates a dose change is needed
  - In the opinion of the investigator the participant would benefit from continued 4-weekly Hgb checks:
    - o as the Hgb is at the upper end of the target range
    - waiting 8 weeks for the next Hgb check is considered too long.
- c. If prolonged QT/QTcF is noted, 2 additional ECG measurements should be obtained and the average QT/QTcF of the triplicate assessment used for eligibility determination. No further ECG monitoring is required, unless as indicated as part of routine care of a participant, see Section 8.2.3.
- d. BP and HR will be assessed with using an appropriate size cuff. BP and HR should be preceded by at least 5 minutes of rest for the participant in a quiet setting without distractions. Three consecutive BP measurements will be obtained, of which the median will be recorded.

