## 4.6. Hemoglobin Target Range and Frequency of Checks

In adults, the dose of daprodustat is adjusted if required, one step at a time in the range of 1 to 24 mg, to ensure the patient's Hgb is within a target range.

In this study, the target range for Hgb is 10 to 12 g/dL, the same for all ages and regardless of dialysis status (ND or D) or within the D sub-trial population, their dialysis modality (PD or HD).

For pediatric patients, nephrologists dose adjust ESA therapy in accordance with both Hgb and clinical response. At Study Weeks 2, 4, 8, 12, 16, 20, 24, 28, 36, 44 and 52, the Hgb will be checked.

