## 8.3.6. Adverse Events of Special Interest

The investigator or site staff will be responsible for detecting, documenting and reporting any events that may represent the AESIs listed below (using preferred terms):

- Death, MI, stroke, HF, thromboembolic events, thrombosis of vascular access.
- Thrombosis and/or tissue ischemia secondary to excessive erythropoiesis.
- New diagnosis of hypertension or worsening of existing hypertension.
- Cancer related mortality and tumor progression and recurrence.
- Esophageal and gastric erosions.

The results of any investigation should be recorded on the AE page and the relevant AESI page of the participant's eCRF.

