## 10.1.2. Adverse Events of Special Interest

The investigator or site staff will be responsible for detecting, documenting, and reporting any events that may represent the AESIs listed below:

- Death, myocardial infarction (MI), stroke, heart failure, thromboembolic events, thrombosis of vascular access.
  - Death
  - o MI
  - o Stroke
  - Heart failure
  - Thromboembolic event
  - Thrombosis of vascular access
- Thrombosis and/or tissue ischemia secondary to excessive erythropoiesis.
- New diagnosis of hypertension or worsening of existing hypertension
  - New diagnosis of hypertension
  - Worsening of existing hypertension
    - New resistant hypertension: hypertension despite treatment with at least 3 (maximal or maximally tolerated doses of) antihypertensive medications.
    - Hypertensive emergency: severely elevated BP associated with acute end-organ damage.

This document is confidential

SAP Version: SAP V1.0 23-Jan-2025

Controlled Document ID: CC Effective Date 31-Aug-2020

Sponsor: GlaxoSmithKline Research & Development Limited; Protocol No.: 214066/Protocol Amendment 02

- Hypertensive urgency: severely elevated BP without the presence of acute endorgan damage.
- Cancer related mortality and tumor progression and recurrence.
- Esophageal and gastric erosions

Potential AESIs will be identified through a pre-defined terms of interest process in which pre-defined lists of AE preferred terms corresponding with each AESI will be used to identify events considered to be potential AESIs. AESI definitions will be added once finalized. Sites will be prompted via query to complete any necessary additional information for these AESIs in the eCRF.

Thrombosis and tissue ischemia events will be considered to be secondary to excessive erythropoiesis if during the window of [AE start date – 30 days, AE start date +15 days] any one of the following 3 events occurs:

- Any Hgb value ≥ 13 g/dL (measured pre-dialysis)
- Hgb increase > 2 g/dL over 2 weeks (+1 week)
  - o Note: for programming purposes, a +1 week window is applied, corresponding to the allowable visit window, to look for increases > 2 g/dL over 3 weeks
- Hgb increase > 4 g/dL over 4 weeks (+1 week)
  - o Note: for programming purposes, a +1 week window is applied, corresponding to the allowable visit window, to look for increases > 4 g/dL over 5 weeks

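### The SAP 10.1.2 rule for thrombosis or ischemia secondary to excessive erythropoiesis has no outcome for events it cannot assess, and 8-weekly Hgb between Weeks 28 and 52 makes such events likely on scheduled data

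*SAP*

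**What the plan says.** SAP 10.1.2 attributes a thrombosis or tissue ischemia event to excessive erythropoiesis on this condition: "during the window of [AE start date – 30 days, AE start date +15 days] any one of the following 3 events occurs". The three are an Hgb of 13 g/dL or more, a rise above 2 g/dL over 2 weeks, and a rise above 4 g/dL over 4 weeks. Each rise gets an extra week in programming, giving limits of 21 and 35 days. For the second rise the SAP explains that "a +1 week window is applied, corresponding to the allowable visit window, to look for increases > 4 g/dL over 5 weeks". To find the rises it takes all Hgb values from 58 days before onset to 15 days after.

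The result feeds the AESI summary (SAP 10.1.4 and Table 3.5). SAP 10.1.3, on missing data, deals only with AE dates. SAP 8.1 keeps unscheduled-visit data out of summary tables.

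Protocol 4.6 sets the Hgb schedule: "At Study Weeks 2, 4, 8, 12, 16, 20, 24, 28, 36, 44 and 52, the Hgb will be checked". The protocol synopsis describes on-treatment visits as "scheduled at 4-weekly intervals up to Week 28, then every 8 weeks up to Week 52", and adds: "There is a Follow-up Visit at Week 56, 4 weeks after the last dose of daprodustat". Protocol 4.6 also calls for an extra Hgb visit at Week 32, 40 or 48 when a listed trigger applies, such as a dose change or a dose hold for high Hgb.

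**The concern.** Two of the three criteria need a pair of Hgb values close together in time, and the third needs at least one value near the event. The rule gives a result when a criterion is satisfied and says nothing when the data to test it do not exist. In a programmed any-one-of-three test, an event that could not be examined ends up in the same place as one that was examined and found negative.

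This matters because AESI incidence is part of the primary endpoint (SAP 5.1), and the schedule is sparsest in the second half of treatment. A reader of Table 3.5 could not tell whether an empty row for this category reflects Hgb that was checked or Hgb that was absent.

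**Working it through.** **Inputs**
- Nominal visit day = 7 × week. Scheduled Hgb: Day 1 and Weeks 2, 4, 8, 12, 16, 20, 24, 28, 36, 44, 52 and 56 (Protocol 1.3 and 4.6).
- Visit windows: ±3 days at Week 2; −7 to +2 days from Week 4. For example, the Week 44 column of the Schedule of Activities reads "Week 44 (-7 to +2 days" (closing bracket omitted).
- Classification window: onset −30 to onset +15 days, i.e. 30 + 1 + 15 = 46 calendar days.
- Pair limits: 21 and 35 days. Look-back: 58 days.

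**The plan's own figure.** The look-back is described as 4 weeks before the window: 30 + 28 = 58 days. This reproduces.

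**Spacing of scheduled pairs**
- 8-weekly: 56 − 9 = 47 to 56 + 9 = 65 days. Even the shortest exceeds 35, so the pairs Week 28–36, 36–44 and 44–52 can never meet either rise criterion.
- 4-weekly: 28 − 9 = 19 to 28 + 9 = 37 days.

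**Dates with no scheduled Hgb in the window.** For an event t days after a visit with the next visit at day g, the window is empty if t > 30 and g − t > 15. That is g − 46 dates.
- g = 56: 10 dates, 10/56 = 17.9%. The three intervals in Weeks 28–52 give 30/168 = 17.9%.
- g = 47: 1/47 = 2%. g = 65: 19/65 = 29%.
- Before Week 28: none.

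**5-week criterion, scheduled data.** The later value must lie in the window, the earlier one no more than 58 days before onset, and the two at most 35 days apart.
- The Week 24–28 pair (days 168 and 196) serves onsets on days 196 to 226: 31 dates, so 31/168 = 18.5% of Weeks 28–52.
- The Week 52–56 pair (days 364 and 392) serves onsets on days 377 to 391: 15 dates, so (31 + 15)/196 = 46/196 = 23.5% of Weeks 28–56.
- Before Week 28: 196/196.

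**3-week criterion, scheduled data.** Only Day 1–Week 2 and Week 2–Week 4 are nominally within 21 days. They serve onsets up to day 28 + 30 = 58, i.e. 59/196 = 30% of dates before Week 28, and none after.

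**Visit windows.** Moving each visit uniformly at random over its allowed days (3,000 runs) gives, for Weeks 28–52, 17.8% uncovered, 15.6% assessable on the 5-week criterion and 0.9% on the 3-week criterion.

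**With every Week 32, 40 and 48 check held.** Uncovered dates fall from 30/168 to 0/168 and the 5-week criterion is assessable on 168/168. The 3-week criterion stays at 0 on nominal dates.

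**Allowance and look-back**
- A compliant 4-weekly pair can be 37 days apart against a limit of 35. The effect is small: with visits moved as above, 98.6% of dates before Week 28 remain assessable on the 5-week criterion, against 100% on nominal dates.
- A pair 35 days apart whose later value falls on onset −30 starts at onset −65, outside the 58-day look-back. The look-back allows 4 weeks and the rule 5.

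**Scale for the enrolled sample.** The documents give no pediatric event rate. Assume per-participant rates from 0.7% (adult thrombosis with excessive erythropoiesis) to 12.4% (adult dialysis thromboembolic events), both from Protocol Table 3, with onset spread evenly over 52 weeks and no extra visits.
- Events expected on an uncovered date: 4 × 0.007 × 24/52 × 10/56 = 0.002 to 4 × 0.124 × 24/52 × 10/56 = 0.04.
- Events expected in Weeks 28–52 with no assessable rise: at most 4 × 0.124 × 24/52 × 137/168 = 0.19, where 137 = 168 − 31.

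**The case against.** The best defence is that the rule does not rely on scheduled data. It takes all Hgb values, and the protocol adds checks where excess Hgb is most likely: after a dose change, after a hold above 12.5 g/dL, after a needed reduction at the lowest step, or when the investigator is concerned about Hgb near the top of the range. Unscheduled visits are possible at any time. This largely stands. It means the 18% is an upper figure for participants with no extra visit, and that those left exposed are mainly stable and in range. It does not give such participants' events an outcome, and it leaves open whether extra and unscheduled values may feed Table 3.5 given SAP 8.1.

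It can also be said that data capture already exists. Protocol 8.3.6 states: "The results of any investigation should be recorded on the AE page and the relevant AESI page of the participant's eCRF". The SAP provides for site queries and names a thrombosis/tissue ischemia eCRF page (SAP 13.3). True, but the SAP does not say that the rule reads Hgb from those pages.

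The one-week allowance is adequate for true 2-week pairs: at most 14 + 3 = 17 days from Day 1 to Week 2, and 14 + 3 + 2 = 19 days from Week 2 to Week 4. It fails only if a Screening sample stands in for Day 1, giving 7 + 14 + 3 = 24 days. The protocol permits this when the two visits are close enough: "Blood tests for eligibility checked at Screening do not need to be repeated if the Day 1 Visit is performed within 7 days of the" first of them. The point does not depend on that case.

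Three stronger readings are tempting and are not supported:
- That no rise criterion can be met on scheduled data after Week 28. The Week 24–28 and Week 52–56 pairs still serve the 5-week criterion.
- That the SAP declares unassessable events not secondary. It is silent; their absence from the category is the effect of the rule as written.
- That the primary endpoint is materially undercounted. Thromboembolic events, access thrombosis, MI and stroke are AESIs in their own category whatever the Hgb, so for them only the sub-classification can change.

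**Conclusion.** The concern holds in a limited form. The rule and the schedule do not fit each other between Weeks 28 and 52. On scheduled data most event dates there cannot be tested for a rise, and about 1 in 6 have no Hgb in the window. The rule has no way to show this. The weakness of the 3-week criterion begins earlier, after the Week 2–Week 4 pair has passed out of the window, and is not caused by the 8-week spacing. The short allowance and look-back are smaller faults of the same kind.

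The percentages assume nominal visit days, event dates spread evenly over the period, and no extra visits. They are shares of dates, not predicted misclassification rates. The population PK analysis plan filed with the SAP (Section 1.1) reports only 4 participants, all adolescents, so an affected event is unlikely. All AEs, all Hgb values and individual Hgb plots are to be produced, so any single case can be checked by eye. Against that, with at most 4 participants in a sub-trial, one event moves a category proportion by at least 1/4, or 25 percentage points. The change is therefore worth making, with modest expectations of its effect.

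**What to change.** In SAP 10.1.2 and the Table 3.5 shell:

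1. Report each thrombosis or ischemia event as met, not met or not assessable. Define not assessable as no criterion met and either no Hgb in the window or no pair within either rise limit. A footnote should say whether the 3-week criterion could be tested. If testable pairs for both rises were required, nearly every event after Week 28 would be not assessable even with all extra checks held.
2. State that Hgb from extra-check visits, unscheduled visits and the AE/AESI eCRF pages counts for this rule, notwithstanding SAP 8.1.
3. Set the limit for 4-weekly pairs to 37 days so that it matches the visit window it cites. Set the look-back to 30 days plus the chosen limit: 30 + 37 = 67 days, or 30 + 35 = 65 if the present limit is kept.

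The cost is a few lines of SAP text and programming, with no change to visits or procedures. The downside is that some events now left out as if not secondary will show as not assessable, and the wider limit slightly loosens the rate-of-rise definition.

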#### Type of Participant and Disease Characteristics:

2. Participants who have anemia associated with CKD as follows:

ND sub-trial	D sub-trial		
CKD stage 3, 4, 5 (not on dialysis) based on eGFR using the bedside Schwartz equation <60 mL/min/1.73m² [Schwartz, 2009]	Prevalent dialysis patients (Stage 5d CKD) defined as those in receipt of maintenance dialysis of ≥30 days duration		
AND			
If not using ESAs, Hgb 7.0 to 11.0 g/dL			
OR			
If using ESAs, Hgb 9.5 to 12.0 g/dL			

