To identify Hgb increases that meet the increase criterion above, all Hgb values taken within [AE start date – 58 days, AE start date + 15 days] will be identified. This corresponds to identifying Hgb values that occurred 4 weeks before the [AE start date – 30 days, AE start date +15 days] window of interest.

A summary table of AESIs by category, sub-categories, and PTs will be provided.

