| Hemoglobin               | MMOL/L (FE)           | G/L     | 16.1134           |
|                          | MMOL/L                | G/L     | 16.1134           |
|                          | G%                    | G/L     | 10                |
|                          | 1000/UL               | GI/L    | 1                 |
|                          | 10^3/UL               | GI/L    | 1                 |
|                          | /MM3                  | GI/L    | 0.001             |
|                          | K/CUMM                | GI/L    | 1                 |
|                          | THOU/CUMM             | GI/L    | 1                 |
|                          | 10^9/L                | GI/L    | 1                 |
|                          | GI/L                  | GI/L    | 1                 |
|                          | CELLS/MM  | GI/L    | 0.001             |
| Platelet Count           | THOU/MCL              | GI/L    | 1                 |
| WBC - Total              | PER CUMM              | GI/L    | 0.001             |
| Lymphocytes              | 10^5/CUMM             | GI/L    | 100               |
| Monocytes
Eosinophils | K/UL                  | GI/L    | 1                 |
| Basophils                | /MCL                  | GI/L    | 0.001             |
| Neutrophils              | /NL                   | GI/L    | 1                 |
| Erythrocytes - RBCs      | 10^3/CUMM             | GI/L    | 1                 |
|                          | KCELLS/UL             | GI/L    | 1                 |
|                          | 10^3/MM3              | GI/L    | 1                 |
|                          | CELLS/UL              | GI/L    | 0.001             |
|                          | 10^4/UL               | GI/L    | 10                |
|                          | 10^6/L                | GI/L    | 0.001             |
|                          | B/L                   | GI/L    | 1                 |
|                          | CELLS/NL              | GI/L    | 1                 |
|                          | THOU/UL               | GI/L    | 1                 |
| MCV                      | FL                    | FL      | 1                 |
| MCH                      | PG                    | PG      | 1                 |
| Deticularita             | 10^12/L               | TI/L    | 1                 |
| Reticulocytes            | 10^6/UL               | TI/L    | 1                 |

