|                          | 10^4/UL               | TI/L    | 0.01              |

This document is confidential.

SAP Version: SAP V1.0 23-Jan-2025 Controlled Document ID: CG E Filing requirements: TMF Effective Date 31-Aug-2020

Sponsor: GlaxoSmithKline Research & Development Limited; Protocol No.: 214066/Protocol Amendment 02

| Laboratory Parameters   | Units     | SI Unit | Conversion Factor |
|---|-----------|---------|-------------------|
|   | CELLS/MM3 | TI/L    | 0.0000001         |
|   | 10^6/CUMM | TI/L    | 1                 |
|   | MIL/MM3   | TI/L    | 1                 |
|   | MILL/MCL  | TI/L    | 1                 |
|   | CELLS/UL  | TI/L    | 0.0000001         |
|   | CELLS/PL  | TI/L    | 1                 |
|   | MILL/UL   | TI/L    | 1                 |
|   | CELLS/NL  | TI/L    | 0.001             |
|   | 10^3/UL   | TI/L    | 0.001             |
|   | K/UL      | TI/L    | 0.001             |
|   | CELLS/MCL | TI/L    | 0.0000001         |
|   | TI/L      | TI/L    | 1                 |
|   | 10^3/CUMM | TI/L    | 0.001             |
|   | GI/L      | TI/L    | 0.001             |
|   | THOU/CUMM | TI/L    | 0.001             |
|   | 10^9/L    | TI/L    | 0.001             |
|   | THOU/UL   | TI/L    | 0.001             |
|   | 10^6/MM3  | TI/L    | 1                 |
|   | /MM3      | TI/L    | 0.0000001         |
| Lymphocytes % Monocytes % Eosinophils % Basophils % Neutrophils % | %         | %       | 1                 |
|   | Ratio     | %       | 100               |

Abbreviations: SI = International System of Units; WBC = White Blood Cell; RBC = Red Blood Cell; MCV = Mean Corpuscular Volume; MCH = Mean Corpuscular Hemoglobin

In the event that a site will only be able to provide WBC count with differential (Neutrophils, Lymphocytes, Monocytes, Eosinophils and Basophils) results in either % or absolute value, the formulas below will be used to convert between results in % and absolute value. Actual values and changes from baseline in both % and absolute value will be summarized by visit. However, the summary of numbers and percentages of participants with normal or abnormal WBC count with differential results and the listing of subjects with any abnormal hematology results will be only based on the original parameter, results of which are reported by sites.

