#### 18.3. Safety

| Number | Table Name  | Analysis
Population |
|--------|---|------------------------|
| 3.1    | Summary of Treatment-Emergent Adverse Events by System
Organ Class and Preferred Term  | (Safety Set)           |
| 3.2    | Summary of Treatment-Emergent Adverse Events Leading to Study
Intervention Discontinuation by System Organ Class and Preferred
Term | (Safety Set)           |
| 3.3    | Summary of Treatment-Emergent Serious Adverse Events by
System Organ Class and Preferred Term  | (Safety Set)           |
| 3.4    | Summary of Treatment-Emergent Serious Adverse Events by
System Organ Class and Preferred Term (Number of Subjects and
Occurrences)  | (Safety Set)           |
| 3.5    | Summary of Treatment-Emergent Adverse Events of Special Interest by Category, Subcategory and Preferred Term                              | (Safety Set)           |
| 3.6    | Summary of Hematology Results by Visit and Changes from Baseline  | (Safety Set)           |
| 3.7    | Summary of Hematology Results Relative to Normal Range, Post-
Baseline Relative to Baseline by Visit                                   | (Safety Set)           |
| 3.8    | Summary of Clinical Chemistry Results by Visit and Changes from Baseline  | (Safety Set)           |
| 3.9    | Summary of Clinical Chemistry Results Relative to Normal Range,
Post-Baseline Relative to Baseline by Visit                            | (Safety Set)           |
| 3.10   | Summary of LFTs (+INR) Results by Visit and Changes from Baseline   | (Safety Set)           |

This document is confidential.

SAP Version: SAP V1.0 23-Jan-2025 Controlled Document ID: CG EFiling requirements: TMF

Effective Date 31-Aug-2020

| Number | Table Name   | Analysis
Population |
|--------|--|------------------------|
| 3.11   | Summary of Vital Signs by Visit and Change from Baseline | (Safety Set)           |

This document is confidential.

SAP Version: SAP V1.0 23-Jan-2025 Controlled Document ID: Effective Date 31-Aug-2020 Filing requirements: TMF

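### Two SAP constants contradict the SAP's own rules: the Hgb look-back stops at day -58 where its 5-week rule needs day -65, and four cell-count factors to TI/L are 10-fold too small

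*SAP*

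**What the plan says.** **Look-back.** SAP 10.1.2 treats a thrombosis or tissue ischemia event as caused by excessive erythropoiesis if any of three Hgb criteria is met between 30 days before and 15 days after the event starts: a pre-dialysis value of at least 13 g/dL, a rise above 2 g/dL over 2 weeks, or a rise above 4 g/dL over 4 weeks. For programming, both rise rules are lengthened by one week to match the visit window. The third becomes an instruction "to look for increases > 4 g/dL over 5 weeks". The next paragraph sets the data to be searched: "all Hgb values taken within [AE start date – 58 days, AE start date + 15 days] will be identified". It explains this range as "identifying Hgb values that occurred 4 weeks before the" window of interest. The result feeds SAP Table 3.5, "Summary of Treatment-Emergent Adverse Events of Special Interest by Category, Subcategory and Preferred Term".

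**Unit factors.** In SAP 10.2, Table 3, the block of rows converting to TI/L (labelled reticulocytes, as far as the extracted text can be read) contains "CELLS/UL | TI/L | 0.0000001". CELLS/MM3, CELLS/MCL and /MM3 carry the same factor. Earlier in the table, for other cell types, stands "CELLS/UL | GI/L | 0.001", and the TI/L block gives a factor of 0.001 from GI/L. Hematology results are reported in SAP Table 3.6, "Summary of Hematology Results by Visit and Changes from Baseline".

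**The concern.** The extra week was added to the rise rule but not to the search range. A program written to the stated range cannot apply the 5-week rule fully: for some qualifying rises the starting Hgb is never retrieved. The error runs one way, since it can remove an attribution to excessive erythropoiesis but never create one. That attribution is an AESI category within the primary safety endpoint and the first risk in Protocol Table 3.

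The gap is reachable within the eligibility criteria. A later value of 13 g/dL or more is generally caught by the first criterion, so a missed rise above 4 g/dL generally starts below 13 - 4 = 9.0 g/dL. ESA users enter at 9.5 to 12.0 g/dL, but for the others Protocol 5.1 allows "If not using ESAs, Hgb 7.0 to 11.0 g/dL".

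The four factors disagree with the rest of their own table. Where a site enters an absolute count in one of those units, the value and its change from baseline in Table 3.6 would be one tenth of the true figure.

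**Working it through.** **Look-back: inputs (SAP 10.1.2).** Window of interest: day -30 to +15. Rules as programmed: above 4 g/dL over 35 days, above 2 g/dL over 21 days. Stated lower limit of the search: day -58.

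1. Reproducing the SAP's figure: -30 - 4 × 7 = -58. It is right for a 4-week rule.
2. The 5-week rule needs -30 - 5 × 7 = -65, so the search is 7 days short.
3. The 3-week rule needs -30 - 3 × 7 = -51, which lies inside -58. Only the 4 g/dL criterion is affected.
4. Let the later value fall on day s (-30 to +15, 46 days) and the earlier value g days before. The pair is lost if s - g < -58. For g = 29, 30, …, 35 this removes 1, 2, …, 7 values of s, a total of 28. The lost pairs end on days -30 to -24. None is lost for g of 28 or less.
5. As a share of day-pairs: 28/(46 × 7) = 28/322 = 8.7% for gaps of 29 to 35 days, and 28/(46 × 35) = 28/1,610 = 1.7% for gaps of 1 to 35 days. With a lower limit of -65, none is lost.
6. Allowing for visit timing: take consecutive 4-weekly visits, each with an offset uniform over the -7 to +2 day window (an assumption), giving 10 × 10 = 100 pairs. The gap is 28 + d, with 10 - |d| pairs at each d.
   - Gaps of 29 to 35 days: 9 + 8 + 7 + 6 + 5 + 4 + 3 = 42 of 100 pairs.
   - Lost pair-days: sum of d(10 - d) for d = 1 to 7 = 9 + 16 + 21 + 24 + 25 + 24 + 21 = 140.
   - Eligible pair-days (gap of 35 days or less): 97 × 46 = 4,462.
   - Share lost: 140/4,462 = 3.1%.

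**Unit factors: inputs (SAP Table 3).** CELLS/UL to GI/L 0.001; GI/L to TI/L 0.001; CELLS/UL to TI/L 0.0000001.

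1. Chaining the first two: 0.001 × 0.001 = 0.000001.
2. Cross-check within the TI/L block: 10^3/UL at 0.001, 10^4/UL at 0.01 and 10^6/UL at 1 each give 0.000001 per cell/µL.
3. Ratio: 0.000001/0.0000001 = 10, the same in all four rows because 1 mm³ = 1 µL. The other 18 rows of the block agree with one another.
4. Example: 50,000 cells/µL becomes 50,000 × 0.0000001 = 0.005 TI/L instead of 0.05 TI/L.
5. Effect on a mean: if one of n participants is affected and true counts are equal (an assumption), the mean is (n - 1 + 0.1)/n of its true value, or 0.9/n too low. That is 22.5% at n = 4, 45% at n = 2 and 90% at n = 1.

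**The case against.** The arithmetic is not in dispute; the case against is about consequence. A miss needs a thrombosis or ischemia event, a rise above 4 g/dL over 29 to 35 days that ends in one particular week, no value of 13 g/dL or more, and no rise above 2 g/dL within 3 weeks. The population PK analysis plan (section 1.1, in the SAP file) says 4 adolescents were enrolled. Thromboembolic events and vascular-access thrombosis still count under the first AESI category, and Listings 16.9 and 16.17 show every adverse event and Hgb value. All of that stands and limits the impact.

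The percentages are shares of day-pairs, not of events or participants. That is fair. The 3.1% describes intervals where both visits have the -7/+2 window, mainly Weeks 4 to 28. Day 1 has no window, so Day 1 to Week 4 is at most 30 days, with a Week 2 value in between; after Week 28 the scheduled visits are 8 weeks apart unless an extra one is triggered.

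For the factors, the finding rests on zeros in a machine-read table whose labels are visibly damaged. A systematic misreading cannot be excluded, although the same value in four separate rows makes it unlikely. Protocol Table 16 lists reticulocytes as a percentage, so absolute counts may not have been collected, and the plan does not say which units sites used.

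Finally, the SAP says AESI definitions are still to be added, and the programs are separate, so what was actually coded is unknown. None of this makes the two specifications consistent.

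**Conclusion.** Both inconsistencies hold. The search range is 7 days too short for the SAP's own 5-week rule, and four TI/L factors are too small by exactly 10.

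For the look-back, the reading assumes that a rise counts when its later value falls in the window, which the SAP implies by searching before day -30. The effect is confined to the excessive-erythropoiesis line of Table 3.5, and tissue ischemia outside the other AESI categories is the case that could go uncounted. For the factors, the effect is confined to absolute counts entered in the four units; the Hgb factors and the GI/L factors for platelets and white cells are correct.

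With 4 participants the chance that either changes a reported result is probably low, but it is not zero, and in such small sub-trials one affected record would shift a mean visibly. These are wrong analysis constants with a specific, nearly free correction, so they should be corrected.

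**What to change.** - In SAP 10.1.2, replace 58 days with 65 days as the lower limit of the Hgb search, and 4 weeks with 5 weeks in the sentence explaining it.
- In SAP Table 3, set the TI/L factors for CELLS/MM3, CELLS/UL, CELLS/MCL and /MM3 to 0.000001, after confirming the printed zeros in the source PDF.
- Carry both changes into the derivation programs. If outputs already exist, check the Hgb dates around any thrombosis or ischemia event, and the units of any absolute reticulocyte counts, for the 4 participants.

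The cost is two constants (one of them repeated in four rows) and one phrase, with no change to design or data collection.

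As a query only, not a claimed error: SAP Table 2 should state whether values recorded as urea are urea by mass or urea nitrogen, because the mg/dL factor of 0.357 fits the latter.
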